5.5 Concomitant Medications and Procedures

All concomitant prescription medications taken during study participation will be tracked in the Clinical Research Information Management System of the NIAID (CRIMSON). For this protocol, a prescription medication is defined as a medication that can be prescribed only by a properly authorized/licensed clinician. Medications to be reported in CRIMSON are concomitant prescription medications, over-the-counter medications and non-prescription medications taken at the time of AEs.

5.6 Prohibited Medications and Procedures

Treatment with other biologics or immunosuppressive or cytotoxic agents will not be permitted unless discussed with and approved by the investigator.

6. Study Schedule

All study assessments/procedures required for each study visit are summarized in Appendix B: Schedule of Procedures/Evaluations. Windows for the study timepoints are specified where appropriate. Blood volumes are given in [Appendix C: Blood Volumes for Specimen Collection](#). Research studies are detailed in [Appendix H: Research Studies](#).

If in-person study visits are limited due to the COVID-19 pandemic, study visits may be rescheduled or study procedures may be modified to allow for continued safety monitoring and data collection for study endpoints remotely. If a visit needs to be rescheduled as a remote visit, a member of the study team will contact subjects with sufficient time prior to the study timepoint to make arrangements. In-person visits may be replaced with or modified to include phone calls, virtual telehealth visits or visits with a local healthcare provider for assessment and sample collection. Mandatory study procedures to be performed at remote visits are indicated for applicable visits throughout section 6. For example, EAE symptom logs can be completed electronically, and blood and/or urine samples may be collected with a local specialist or healthcare provider and sent in for clinical and research analyses. However, some research blood cannot be shipped and would be waived based on the discretion of the principal investigator. Regular phone or virtual calls will occur (as per the assessment schedule or more frequently if needed) for safety monitoring and discussion of the subject's health status until the subject can again visit the site.

6.1 Enrollment (Visit 1)

Screening of subjects for this study will occur under NIH protocol 94-I-0079 (“Eosinophil activation and function in parasitic infections and other conditions with increased tissue or peripheral blood eosinophilia in humans”).

Subjects with EAE will be brought in for enrollment (Visit 1). Visit 1 may occur over several days.

After signed informed consent is obtained, the following procedures and laboratory tests will be performed:

- Complete history and physical examination, including limb measurements
- Vital signs, including weight
- Photography (with infrared thermography if available)
- CBC with differential
- Routine laboratory testing, including acute care panel, hepatic panel, mineral panel, lactate dehydrogenase (LDH), creatine kinase (CPK), C-reactive protein (CRP), and urinalysis

- Serum tryptase, aldolase, and quantitative immunoglobulin levels (including IgE)
- Urine pregnancy test (females of childbearing potential only)
- Collection of serum or plasma and urine for immunologic analyses and quantification of eosinophil granule proteins
- Collection of whole blood for isolation and storage of plasma and cells for research studies
- Whole blood lymphocyte phenotyping by T-, B-, and natural killer-cell analysis (TBNK) and RNA sequencing (RNAseq)
- Optional bone marrow biopsy and aspiration, if not available under protocol 94-I-0079 or another NIH protocol
- Optional skin punch biopsy
- AE assessment

The subjects will start a log of symptoms of EAE that they will fill out daily to track symptoms, weight, and temperature. They will also start daily and monthly patient-reported outcome measures for angioedema symptoms and quality of life at this time. These logs and measures will be completed electronically using REDCap. Subjects will discontinue daily logs and measures after the third mepolizumab visit (Visit 7) but will continue monthly measures through the end of the primary study phase (section [7.1.2](#)).

After this visit, subjects will also begin 2-3X/week lab blood draws locally to assess cycles and blood counts between visits. Frequency of weekly labs may be adjusted to avoid exceeding NIH CC blood volume limits (2X/week for subjects with shorter cycles or after peak AEC is reached). Blood will be drawn for CBCs (performed at local lab with results sent to NIH), and urine will be collected and mailed to the NIH for research evaluations. These local blood and urine collections will continue between scheduled study visits through Visit 6. Estimated total number of blood draws is approximately 3X/week for 2 months (approximately 24 blood draws) while not at NIH.

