LDH	Lactate Dehydrogenase
LPD	Laboratory of Parasitic Diseases
N	Number (typically refers to number of subjects/sample size)
NIAID	National Institute of Allergy and Infectious Diseases
NIH	National Institutes of Health
OHSRP	Office of Human Subjects Research Protections
PBMC	Peripheral Blood Mononuclear Cell
RNAseq	RNA sequencing
SAE	Serious Adverse Event
SC	Subcutaneous
TBNK	T-, B-, and Natural Killer–Cell Analysis
UP	Unanticipated Problem
U.S.	United States

Protocol Summary

Full Title:	Pilot Study of Mepolizumab in Episodic Angioedema with Eosinophilia
Short Title:	Mepolizumab in EAE
Sample Size:	N = 12
Accrual Ceiling:	15
Study Population:	Adult subjects with confirmed episodic angioedema with eosinophilia (EAE)
Accrual Period:	2 years
Study Design:	
This will be an open-label pilot study. Following completion of eligibility assessments, subjects with confirmed EAE will enter a run-in period, during which the periodicity of their cycle will be assessed (if not known) and the optimal timing of the baseline visit will be determined. During this time, subjects will begin daily and monthly patient-reported outcome measures; the daily measures will be continued for about 3 months (through the third mepolizumab dose), and the monthly measures will be continued through the end of the primary study phase. Also, subjects will begin visiting a local lab 2-3X/week for collection of blood for complete blood count (CBC) with differential and serum and urine to be mailed to NIH for research; local lab visits will continue between study visits through the second mepolizumab administration. Once cycling and periodicity is confirmed, the baseline visit will be scheduled at the predicted neutrophil peak. Baseline assessments will include history and physical examination, routine laboratory testing, and whole blood flow cytometric analysis. Subjects will again be evaluated and have bloodwork during their predicted eosinophil peak (may be concurrent with baseline if peak eosinophils and neutrophils occur <1 week apart) and at the next predicted eosinophil nadir; at the nadir visit, they will receive their first administration of mepolizumab (700 mg via intravenous [IV] infusion). Subjects will return to the NIH at the predicted neutrophil peak for clinical evaluation and whole blood flow cytometry.

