3.1 Description of the Study Design

Subjects with proven EAE will be invited to participate in the study. The timing of visits for each individual subject will be determined based on the periodicity of cycles in that subject (section [3.2, Figure 1](#)). Screening will be performed on NIH protocol 94-I-0079. Potential study subjects with EAE who have not previously been studied at NIH or who are on a new treatment regimen may be asked to undergo blood draws 2-3 times per week for several weeks on protocol 94-I-0079 to a) confirm the diagnosis and cycling with peak absolute eosinophil count (AEC) $>1500/\text{mm}^3$ and b) to determine presence of symptoms associated with EAE since subjects will need to have symptoms to enroll. Subjects who no longer cycle or who have controlled disease on prednisone or other agents may taper their current therapy 3 months prior to screening under the direction of their primary doctor to meet entry criteria before enrolling in this study.

If an EAE patient has eosinophilia and symptoms on current therapy and agrees to join the study, they will be brought in for an enrollment visit (Visit 1) for initial evaluation. After the enrollment visit, subjects will begin a daily symptom and weight log ([Appendix E: Patient Symptom Log](#)) and daily and monthly assessments of angioedema symptoms using validated angioedema activity and quality of life scales ([Appendix F](#)). Logs and assessments will be collected electronically using REDCap and continued as described in section [7.1.2](#). Also, between study visits, subjects will have 2-3X/week collection of blood for CBC with differential and serum and urine for cytokine and mediator analysis. These blood and urine collections will continue between study visits until Visit 6.

Once cycling and periodicity is confirmed, the baseline visit (Visit 2) will be scheduled at the predicted peak absolute neutrophil count (ANC), and ideally while eosinophils have not yet risen. Baseline assessments will include history and physical examination, routine laboratory testing, and whole blood flow cytometric analysis.

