3.2 Study Schematic

A general schematic for the primary and secondary assessments on the study is given below. Cycle duration varies between subjects, but is approximately 4-6 weeks (examples of cycle length determination based on data from individual subjects are given in [Appendix D: Cycle Length Determination for 3 Patients](#)). Study dose de-escalation is not shown.

[figure not shown]

Figure 1. Study Schematic.

The black arrows indicate study visits (V) for blood draws and clinical assessments, the purple arrows indicate mepolizumab infusions, and the blue bars indicate interval blood draws being performed locally. The estimated timing of visits is indicated in approximate days (~D). The asterisks (*) and (**) define the comparison timepoints for the secondary efficacy endpoint. Subjects will document their weight, temperature, and symptoms and severity every day for about 3 months after enrollment. V8 will begin the Dose De-escalation Phase for subjects who receive benefit from mepolizumab.

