3.3 Study Endpoints

3.3.1 Primary Endpoint

Reduction in the number and severity of clinical symptoms associated with EAE after 3 doses of mepolizumab (as compared to symptoms logged in the approximately monthly cycle preceding initiation of mepolizumab).

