7.1.2 Photography and Infrared Thermography

Full or partial body photographic documentation of skin and musculoskeletal involvement will be obtained at enrollment (Visit 1), baseline (Visit 2), and Visit 5 as well as if clinically indicated. Infrared thermography may be used to assess extent of skin involvement using a gradation of colors to demonstrate emission of heat, or thermal radiation, emitted from a surface, if available. Subjects will be asked to refrain from eating for 4 hours prior to thermography so pictures can be compared in the future. The room may also be kept cooler than usual (about 22°C or 72°F) during infrared thermography. Images will be analyzed, transmitted, and stored securely to maintain confidentiality and privacy of subjects.

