7.1.3 Symptom Logs and Patient-reported Outcomes

Patients will fill out a daily log capturing symptoms, weight, and temperature (Appendix E: Patient Symptom Log), and fill out validated patient-reported outcome measures for angioedema (daily) and quality of life (monthly; questionnaires provided as [Appendix G](#)). These logs and measures will be completed electronically using REDCap. Subjects will also be encouraged to notify the investigators of any new signs or symptoms that develop between study visits. The daily logs and measures will be completed through the end of study endpoint assessments (Visit 8). For subjects in the de-escalation phase, after Visit 8 until study completion, weekly angioedema and monthly quality of life questionnaires will be continued, and weekly symptoms logs ([Appendix F](#)) will be completed.

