Key: AE- adverse event; AEC- absolute eosinophil count; ANC- absolute neutrophil count; CBC- complete blood count; CPK- creatine kinase; IgE- immunoglobulin E; LDH- lactate dehydrogenase; PBMC- peripheral blood mononuclear cell; PROs- patient-reported outcome measures; TBNK- T, B, and natural killer cell; UV- unscheduled visits; ¹ Study visits may be rescheduled or study procedures may be waived or modified to be performed remotely due to travel limitations or safety concerns during the coronavirus disease 2019 pandemic (as described in protocol section 6); ² All subjects will complete Visit 8. Subjects who experienced benefit from mepolizumab administration will continue in the de-escalation phase (which begins with additional procedures at Visit 8—see Table 2 below); for subjects who do not continue in the de-escalation phase, Visit 8 will be the final study visit. ³ The exact timing of Visit 1 through Visit 5 may vary from this schedule based on subject cycle times. Visits 2 and 3 may be combined if neutrophils and eosinophils peak <1 week apart. Every effort will be made to schedule Visit 5 in advance of Visit 6; in the event that Visit 5 occurs within 1 day of Visit 6, only collection of whole blood for storage will be performed for Visit 5. Visits 6, 7, and 8 will be scheduled monthly based on the timing of Visit 4. ⁴ Urine pregnancy test prior to administration of mepolizumab in women of child-bearing potential; ⁵ Performed electronically via REDCap. Symptom logs to be performed daily; PROs daily and monthly, not only at study visits; daily symptom logs and measures will be discontinued after Visit 7, and monthly questionnaires will be continued through Visit 8; ⁶ Home labs will be done 2-3X/week, depending on subject cycle times (2X/week in some cases or after peak is obtained); ⁷ Optional. Bone marrow will be requested to be performed only once at Visit 1 or 2, if a sample is not available from another NIH protocol. Skin punch biopsy will be requested to be performed only once on Visits 1, 2, or 3; ⁸ May be requested once at any time while on study drug if a pre-treatment sample was collected/available.

Table 2. Schedule of Procedures/Evaluations for the De-escalation Phase.

Evaluations	Study Drug 500 mg	Study Drug 500 mg	Study Drug 500 mg	Study Drug 300 mg	End of De-escalation	UV			
Visit Number	8	9	10	11	12	13	14		
Day (assuming 4-week cycle)	Day 99	Day 127	Day 155	Day 183	Day 211	Day 239	Day 267		
Window (days)	±7	±7	±7	±7	±7	±7	±7		

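### Section 6.1 and Table 1 end daily symptom logging at Visit 7, section 7.1.3 at Visit 8; under the Visit 7 text the primary endpoint has no daily score after dose 3

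*Combined protocol and SAP*

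**What the plan says.** Four places point to Visit 7, the visit at which the third 700 mg dose is given (section 5.4):

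- Section 6.1: "Subjects will discontinue daily logs and measures after the third mepolizumab visit (Visit 7".
- Appendix B, Table 1 footnote: "daily symptom logs and measures will be discontinued after Visit 7, and monthly questionnaires will be continued through Visit 8".
- Protocol Summary, Study Design: "the daily measures will be continued for about 3 months (through the third mepolizumab dose".
- Section 3.2, Figure 1 legend: "Subjects will document their weight, temperature, and symptoms and severity every day for about 3 months after enrollment". No visit is named, but the duration fits Visit 7 better (see the working).

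One place explicitly says Visit 8. Section 7.1.3: "The daily logs and measures will be completed through the end of study endpoint assessments (Visit 8".

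The cross-references do not settle it. Section 3.1 says "Logs and assessments will be collected electronically using REDCap and continued as described in section" 7.1.2, and section 6.1 cites the same number, but that section is headed "7.1.2 Photography and Infrared Thermography". The log text is in 7.1.3.

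The primary endpoint (section 3.3.1) is "Reduction in the number and severity of clinical symptoms associated with EAE after 3 doses of mepolizumab", compared with the cycle before treatment. Sections 3.1 and 6.3.6 place its assessment at Visit 8, one month after dose 3. Section 15.1 analyses it as the maximum DAES per cycle in a quasi-Poisson model.

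**The concern.** All of these statements are current text and they cannot all be followed. The difference is the whole interval between Visits 7 and 8, the only period that follows the third dose before the endpoint is assessed.

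Nothing else collected in that interval stands in for a daily score. The weekly log starts at Visit 8, and only for subjects who enter de-escalation (section 6.4.1). The monthly AE-QoL is a four-week recall of restriction and burden (Appendix G). The Visit 8 history and AE assessment do not give daily severity ratings. The daily angioedema measure would stop as well, because the Visit 7 text covers measures as well as logs.

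Unrecorded diary days cannot be recovered. If the electronic diary is built to the Visit 7 text, every subject is affected. The checklists might not catch it: Visit 7 reviews adherence to the monthly measures only (section 6.3.5), and Visit 8 lists no log review (section 6.3.6).

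**Working it through.** **Days.** Table 1 (4-week cycle) puts Visit 1 at Day -30 to -15, Visit 4 (dose 1) at Day 15, Visit 7 (dose 3) at Day 71 and Visit 8 at Day 99. Sections 6.3.4 to 6.3.6 set each visit 28 days after the one before, with windows of ±5 (Visit 6), ±5 (Visit 7) and ±7 (Visit 8).

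- Enrolment to Visit 7: 71+15 = 86 to 71+30 = 101 days. To Visit 8: 99+15 = 114 to 99+30 = 129 days. About three months fits the first.
- Logged time on drug with a Visit 7 stop: 71-15 = 56 days; 56 ± (5+5) = 46 to 66.
- With a Visit 8 stop: 99-15 = 84 days; 84 ± (5+5+7) = 67 to 101.
- Missing interval: 28 ± 7 = 21 to 35 days.
- Post-treatment cycles at 28 days each: 56/28 = 2 against 84/28 = 3. At 42 days: 1.33 against 2.

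**Effect on the estimate.** Let S0 be the sum of baseline scores, S1 the sum of post-treatment scores and K the number of post-treatment cycles. With fixed person effects and equal windows, the fitted reduction is 1 - (S1/K)/S0, so it averages over the cycles logged. It is unchanged if the effect is constant. With assumed reductions after doses 1/2/3:

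| Assumed reductions | Visit 7 stop | All three intervals | After dose 3 |
|---|---|---|---|
| 50/70/90% | (50+70)/2 = 60% | (50+70+90)/3 = 70% | 90% |
| 90/70/50% | (90+70)/2 = 80% | (90+70+50)/3 = 70% | 50% |

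**Power.** Inputs from section 15.1: person mean gamma (mean 3, variance 3), extra variation gamma (mean 1, variance 0.25), Poisson counts, 87.5% reduction, dispersion not allowed below 1, t-based two-sided 95% interval. The log ratio is log[(S1/K)/S0], with standard error sqrt[φ(1/S0+1/S1)], φ = max(1, Pearson X²/df) and df = n(K+1)-n-1, which is 14 for n=5, K=3 and 9 for n=5, K=2. This closed form matched a fitted GLM. There were 200,000 simulated trials per setting (100,000 at n=12). Trials with all post-treatment scores zero count as not significant (1.0% at n=5, K=3; 4.0% at n=5, K=2).

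The plan's own figures reproduce first. With no effect, n=5 and K=3, type I error is 4.9% two-sided and 3.6% one-sided (stated 4.9% and 3.4%).

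| Setting | Power | Shows at least a 30% reduction |
|---|---|---|
| n=5, 1+3 cycles | 91.1% (stated over 91%) | 79.9% (stated 80%) |
| n=5, 1+2 cycles | 78.4% | 59.6% |
| n=12, 1+2 cycles | 99.9% | 98.9% |

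For n=5 with 1+2 cycles, counting all-zero trials as significant gives 82.5% and 63.7%. Leaving subjects with no symptoms in any cycle out of the df gives 71.9% and 53.2%. With only one complete post-treatment cycle, a separate run of 40,000 trials gives 17% at n=5 (36% counting all-zero trials as successes) and 95% at n=12.

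**The case against.** The strongest objection is that Visit 8 logging does not by itself deliver an effect after dose 3. The model in section 15.1 gives one common reduction to all post-treatment cycles. In the 50/70/90% illustration, logging to Visit 8 yields 70%, not 90%. The endpoint wording can also be read as the whole three-dose course, in which case a Visit 7 stop loses one interval of three. This stands as a limit on what the fix achieves. It does not remove the defect: on either reading the interval after dose 3 belongs to the endpoint, and without it no analysis can show whether the effect holds, builds or wanes.

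Second, the 78% holds only for 4-week cycles. Section 3.2 gives 4 to 6 weeks, and section 6.3.3 says the drug may alter cycle times. At 6 weeks, Visit 8 gives two complete post-treatment cycles (about 78% at n=5) and Visit 7 gives one (about 17%). This stands, and any restated power must carry the condition.

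Third, Visit 8 has more support than section 7.1.3 alone. Section 6.4.1 changes the log from daily to weekly at Visit 8 and speaks of continuing the patient-reported measures. True, and it favours the proposed direction, but section 6.1 still names Visit 7.

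Fourth, the Table 1 footnote schedules Visits 6 to 8 from Visit 4, which would narrow the ranges to 51–61 and 77–91 days. Sections 6.3.4 to 6.3.6 chain each window to the previous visit, so the wider ranges are kept. The nominal 56 and 84 days do not change.

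**Conclusion.** The contradiction is real and falls on the primary endpoint, so it must be resolved. Under the Visit 7 text no daily score of any kind exists for about 28 days after dose 3, at any sample size, and the primary estimate would rest on doses 1 and 2.

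Power is secondary. With 4-week cycles unchanged on drug and an 87.5% reduction, it falls at n=5 from about 91% to about 78% (72% to 82% depending on the handling of all-zero data and df). At the planned n=12 the loss is negligible.

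The documents do not name the source of the DAES. That it is the daily log is an inference from the endpoint's reference to logged symptoms, but the conclusion does not depend on it, because the daily log and the daily measures stop together. How the diary was actually configured is not in the documents.

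**What to change.** 1. Amend the Protocol Summary, the Figure 1 legend in section 3.2, section 6.1 and the Table 1 footnote to agree with section 7.1.3: daily log and daily measures through Visit 8 for all subjects. This follows the less frequent text because the endpoint needs it.
2. Add review of the daily log to the Visit 7 and Visit 8 procedure lists (sections 6.3.5 and 6.3.6).
3. Correct the cross-reference from 7.1.2 to 7.1.3 in sections 3.1 and 6.1.
4. State in section 3.3.1 whether the endpoint means the interval following dose 3 or the whole three-dose course, since the model averages over all post-treatment cycles.

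If Visit 7 is kept instead, reword the endpoint to the period after doses 1 and 2. Restate the n=5 power as about 78% (about 60% for showing at least a 30% reduction) under 4-week cycles, note that one complete post-treatment cycle gives about 17%, and put the n=12 figures beside them.

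The cost is protocol wording plus about 28 more days of an electronic diary already in use, with no added visits or samples.

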6.2 Baseline (Visit 2, Day 0)

The baseline visit (Visit 2) will be scheduled to coincide with the estimated peak ANC based on data from prior cycles. If the ANC begins to rise prior to the scheduled baseline visit, the subject will be brought back to NIH as soon as feasible. For subjects whose ANC peak and AEC peak are closer together than a week, Visits 2 and 3 may be combined.

The following procedures and laboratory tests will be performed at the baseline visit:

- Complete history and physical examination, including limb measurements
- Vital signs, including weight
- Photography (with infrared thermography if available)
- Review of symptom/weight logs and patient-reported outcome measures adherence
- CBC with differential
- Routine laboratory testing, including acute care panel, hepatic panel, mineral panel, CRP, and urinalysis
- Serum tryptase, aldolase, and quantitative immunoglobulin levels (including IgE)
- Collection of serum or plasma and urine for immunologic analyses and quantification of eosinophil granule proteins
- Collection of whole blood for isolation and storage of plasma and cells for research studies
- Collection of whole blood for TBNK and RNAseq
- Optional bone marrow biopsy and aspiration, if not done at the enrollment visit or available under protocol 94-I-0079 or another NIH protocol
- Optional skin punch biopsy, if not done at the enrollment visit (Visit 1)
- AE assessment

